4.3. Exclusion Criteria

Individuals who meet any of these criteria are not eligible for enrollment as study participants in Phase 1a and Phase 2:

1. Are pregnant or lactating. Post-menarcheal females must be abstinent or use a medically acceptable birth control method throughout the study (e.g. oral, subcutaneous, mechanical, or surgical contraception).
2. Cannot perform spirometry at Screening.
3. Have an asthma severity classification at Recruitment of severe persistent, using the NAEPP classification, as evidenced by at least one of the following:
 - a. Require a dose of greater than 500 mcg of fluticasone per day or the equivalent of another inhaled corticosteroid.
 - b. Have received more than 2 courses of oral or parenteral corticosteroids within the last 12 months or one course within the last 3 months.
 - c. Have been treated with depot corticosteroids within the last 12 months.
 - d. Have been hospitalized for asthma within the 12 months prior to recruitment.
 - e. Have had an emergency room visit for asthma within the 3 months prior to recruitment.
 - f. Have had a life-threatening asthma exacerbation that required intubation, mechanical ventilation, or that resulted in a hypoxic seizure within 2 years prior to recruitment.
4. Have nasal polyps or other major structural abnormalities in their nasal cavities as assessed by anterior rhinoscopy.
5. Have active rhinitis symptoms prior to the nasal allergen challenge, defined as a Baseline TNSS >3 , with no individual symptom score >1 .

6. Do not have access to a phone (needed for scheduling appointments).
7. Have received allergen immunotherapy (SLIT or SCIT) in the last 12 months prior to recruitment or who plan to initiate or resume allergen immunotherapy during the study.
8. Have previously been treated with anti-IgE therapy in the 12 months prior to recruitment.
9. Are currently receiving oral or nasal antihistamines, nasal corticosteroids, nasal decongestants, nasal anticholinergics or cromolyn, which cannot be suspended for the required washout periods prior to skin prick testing and the nasal allergen challenge.
10. Have received an investigational drug in the 30 days prior to recruitment or who plan to use an investigational drug during the study.

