8.1. Recruitment

The study centers may use any IRB-approved means to identify potential participants. Examples include hospital, clinic, or emergency department admission records; investigators' specialty clinic records; and advertising (in public locations and on the radio). Potential participants will be screened and recruited using a standardized questionnaire that collects contact information and inclusion/exclusion criteria information. Participants may be recruited by phone or in person.

Retention methods involve a number of different approaches. Appointment reminder cards are given at each visit. We will use an appointment reminder system that consists of phone calls and/or text messages several days and one day prior to scheduled appointments for confirmation. To facilitate telephone contact with subjects whose phone service may change during the study, at least three telephone contact numbers (relatives, neighbors, friends) will be collected for each subject. This has proven to be an effective strategy in previous ICAC studies. Those who have no obvious characteristics making them ineligible and who are interested will be invited to the clinic for a Screening Visit.

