8.4. Repeat Challenge Visit – Phase 1b

In order to participate in the Repeat Challenge Visit, Phase 1a participants must meet the following evaluation criteria:

- The participant's asthma must be well controlled as defined by:
 - A FEV1 greater than or equal to 80% predicted (see Section 8.2).
 - An Asthma Control Test (ACT) score ≥ 20 .
- The participant tolerated the NAC during Phase 1a with no AEs grade 2 or above as determined by Table 12.3.1a Grading of Local Reactions to Study Procedures.

Phase 1a participants will be excluded from participation in the Repeat Challenge Visit if any of the following criteria are met:

- Are pregnant or lactating.

- Have an asthma severity classification of severe persistent, using the NAEPP classification, as evidenced by at least one of the following:
 - Require a dose of greater than 500 mcg of fluticasone per day or the equivalent of another inhaled corticosteroid.
 - Have received more than 2 courses of oral or parenteral corticosteroids within the last 12 months or one course within the last 3 months.
 - Have been treated with depot corticosteroids within the last 12 months.
 - Have been hospitalized for asthma within the 12 months prior to their participation in Phase 1b.
 - Have had an emergency room visit for asthma within the 3 months prior to their participation in Phase 1b.
 - Have had a life-threatening asthma exacerbation that required intubation, mechanical ventilation, or that resulted in a hypoxic seizure within 2 years prior to their participation in Phase 1b.
- Have received allergen immunotherapy (SLIT or SCIT) in the last 12 months prior to their participation in Phase 1b.
- Have previously been treated with anti-IgE therapy in the 12 months prior to their participation in Phase 1b.
- Are currently receiving oral or nasal antihistamines, nasal corticosteroids, nasal decongestants, nasal anticholinergics or cromolyn, which cannot be suspended for the required washout periods prior to the nasal allergen challenge in Phase 1b.
- Have received an investigational drug in the 30 days prior to their participation in Phase 1b.

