8.9. Visit Windows

Study visits should take place within the time limits specified below: the designated visit windows (*i.e.* $+- n$ days) for each scheduled visit are also indicated on the Schedule of Events. Additional details are provided in the MOP for Protocol ICAC-27.

The Challenge Visit should be conducted within 2 months of the screening visit. Participants unable to return for the Challenge Visit within 2 months of the Screening Visit will need to have the medical history, physical exam and urine pregnancy test (if applicable) repeated prior to initiation of the NAC. Participants may be reevaluated up to a maximum of 2 times for the Phase 1a and Phase 2 Challenge Visits if they are ineligible due to nasal symptoms or other reversible illness if their condition improves within 2 months of the Screening Visit.

A Follow-Up Phone Visit should occur approximately 24 hours after the end of a Challenge Visit (as described in the MOP for Protocol ICAC-27). In a subset of sites in Phase 1a, Phase 1b, and Phase 2, a Follow-Up Clinic Visit may occur in lieu of the phone call (see MOP for Protocol ICAC-27 for details). A Follow-Up Clinic Visit should occur 6 to 10 days after the Challenge Visit for participants who have agreed to participate in the mechanistic blood draw. Another Follow-up Phone Visit should occur 6 to 10 days following a challenge if the participant is not seen at the study site at this time (as described in the MOP for Protocol ICAC-27).

The optional Phase 2 30-day Follow-Up Visit should occur 30 days after the Challenge Visit (as described in the MOP for Protocol ICAC-27).

The Phase 1b Repeat Challenge Visit should be conducted within 30-365 days after the Challenge Visit. Participants may be reevaluated up to a maximum of 3 times for the Phase 1b Repeat Challenge Visit if they are ineligible due to nasal symptoms or other reversible illness if their condition improves during the 365 days after their initial Challenge Visit.

The Phase 1b 30-day Follow-Up Visit should occur 30 days after the Repeat Challenge Visit (as described in the MOP for Protocol ICAC-27).

9. Mechanistic Assays

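### For the Phase 2 children, the asthma-severity exclusion is dated from recruitment rather than the challenge, and the protocol attaches no FEV1 entry limit to the challenge-day spirometry

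*Protocol*

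**What the plan says.** **Phase 1a and Phase 2 (Protocol 4.3, exclusion 3).** The stem reads: "Have an asthma severity classification at Recruitment of severe persistent, using the NAEPP classification, as evidenced by at least one of the following". The emergency-visit item reads: "Have had an emergency room visit for asthma within the 3 months prior to recruitment". The hospitalization item (12 months) and the life-threatening-exacerbation item (2 years) are dated the same way. The oral and depot steroid items have no date of their own and take it from the stem.

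**Phase 1b (Protocol 4.3 and 8.4).** The same list opens without the recruitment anchor: "Have an asthma severity classification of severe persistent, using the NAEPP classification, as evidenced by at least one of the following". Its emergency-visit item reads: "Have had an emergency room visit for asthma within the 3 months prior to their participation in Phase 1b". FEV1 of at least 80% predicted and ACT of at least 20 are introduced by: "In order to participate in the Repeat Challenge Visit, Phase 1a participants must meet the following evaluation criteria".

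**Sequence of visits.** Recruitment comes before screening. Section 8.1 says: "Those who have no obvious characteristics making them ineligible and who are interested will be invited to the clinic for a Screening Visit". Section 8.9 asks for the challenge within 2 months of screening and prints no outer limit. Participants who come later "will need to have the medical history, physical exam and urine pregnancy test (if applicable) repeated prior to initiation of the NAC". Spirometry is not on that repeat list. Section 8.7 shows that a same-day challenge is possible.

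**Lung function.** Section 8.2 applies the FEV1 limit at screening. Section 8.3 admits participants to the challenge on their Screening Visit results, and its item 3 includes spirometry at the Challenge Visit without a pass value. Section 5.1.1 names the exclusion of people below 80% predicted as a way to reduce the risk of provoking asthma.

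**The concern.** The second primary objective is the safety profile of the challenge in children with asthma, whom the entry criteria require to be well controlled. Section 4.1 says that tolerability in children with asthma is unknown. An entry criterion protects a child only if it still holds when the allergen is given. As written, a child who had an emergency visit or a course of oral steroid after recruitment passes exclusion 3. A child whose FEV1 is below 80% predicted on the challenge day meets no stated bar to starting. Either decision is left to judgement at the five sites named in SAP 7.1.1.

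There is little room for a poor decision. Under Protocol 11.5, one nonfatal SAE possibly related to the product suspends the study, as do related falls in lung function of the defined size in two participants.

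**Working it through.** The plan gives no figure to reproduce. The check compares texts and adds simple arithmetic.

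**1. The two versions of the severity exclusion**

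| Item | Phase 1a and Phase 2 (4.3) | Phase 1b (4.3, 8.4) |
|---|---|---|
| Stem | at recruitment | no date |
| Oral and depot steroid | date taken from the stem | no date |
| Hospitalization, 12 months | before recruitment | before Phase 1b participation |
| Emergency visit, 3 months | before recruitment | before Phase 1b participation |
| Life-threatening exacerbation, 2 years | before recruitment | before Phase 1b participation |

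The list was re-dated for the adults' repeat challenge. For the children's first challenge it was not. Section 3.1 reports the Phase 1a outcome, so in practice the recruitment-dated version now governs only Phase 2.

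**2. How much of the period before the challenge is covered**

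Let g be the months from recruitment to challenge and L the length of a look-back. The part of the last L months before the challenge that the written look-back covers is max(0, L − g).

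- L = 3 (emergency visit; one steroid course): g = 0 gives 3 of 3; g = 1 gives 2; g = 2 gives 1; g = 3 or more gives 0.
- L = 12 (hospitalization; depot steroid; more than two courses): g = 2 gives 12 − 2 = 10 of 12.
- L = 24 (life-threatening exacerbation): g = 2 gives 24 − 2 = 22 of 24.

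Because recruitment precedes or coincides with screening, g is at least the screening-to-challenge interval. The value g = 2 is the edge of the 8.9 window when recruitment and screening coincide. It is not offered as typical, and the documents give no actual gaps. The loss falls mainly on the 3-month items.

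**3. FEV1 on the day**

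The measurement is taken (8.3 item 3), but no entry value is attached to it. By contrast, nasal symptoms do have a challenge-day limit (4.3 item 5; 8.3 item 7).

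The stops during the challenge (8.3 items 9 and 11) are relative: a PEF fall of more than 20% from baseline suspends it, and FEV1 below 85% of baseline stops it. As an illustration, assume that the FEV1 baseline is the same-day value. A child starting at 80% predicted reaches the FEV1 stop below 0.85 × 80 = 68% predicted. One starting at 70% reaches it below 0.85 × 70 = 59.5%. These rules limit a fall; they do not decide who starts.

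**4. Whether another provision closes the gap**

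- Exclusion 11 (4.3) and physician discretion (8.2) rest on judgement.
- The withdrawal reasons in 11.2 are permissive. The one on inhaled steroid concerns a dose above 500 mcg needed to maintain control, not a single emergency visit or oral course.
- Section 7.3 does not list oral steroids as prohibited or as needing a washout.
- Re-evaluation for reversible illness under 8.9 names neither FEV1 nor an exacerbation.

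None of these sets an asthma entry limit for the challenge day.

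**The case against.** The strongest reply is that item 3 describes the study population. Classifying severity at entry is ordinary, and acute fitness is handled elsewhere. Challenge-day spirometry, lung examination, and review of adverse events and medication are all required (8.3). Re-evaluation under 8.9 presupposes an eligibility judgement at that visit that goes beyond nasal score. Adverse events are collected from consent, and a hospitalization would be reported as an SAE within 24 hours. Phase 1b needed new dates because it runs 30 to 365 days after the first challenge and 8.4 describes no new screening visit. All of this is true, and it makes an unsafe challenge less likely. It still leaves a written exclusion that a post-recruitment event does not trigger, with only discretion in its place.

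Several stronger readings are tempting but are not supported:

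- **That FEV1 applies only at screening.** The timing is unclear. Section 5.1.1 names no visit, and the cross-reference to 8.2 also appears in the Phase 1b criterion. A site could apply the limit on the day; no sentence requires it.
- **That ACT was left out of the challenge.** Section 8.2 does not name ACT either, and Phase 1b requires ACT while following the 8.3 list that omits it. These lists do not show when ACT is done.
- **That 8.4 sets a challenge-day rule.** It ties the criteria to taking part in the repeat challenge but names no day.
- **That 7.1.2 permits challenging a child in exacerbation.** Its allowance for short-term high-dose inhaled steroid also covers the period after the challenge.

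**Conclusion.** The point holds in limited form. For Phase 2, exclusion 3 looks back from recruitment, so events between recruitment and the challenge fall outside it. The protocol text also attaches no FEV1 entry limit to spirometry done on the challenge day. This should be fixed: it concerns a primary safety objective in children, and the criteria and the measurement already exist.

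The only size that can be stated is coverage. At a two-month gap, one of the three months before the challenge is covered by the 3-month look-backs; from three months, none is. A reader might infer that children were challenged while unstable, or that events will be more frequent. The documents give neither actual gaps nor a rate of worsening, so neither inference is supported. The conclusion is limited to the protocol text; the Manual of Procedures and Schedule of Events were not available and may contain a challenge-day rule.

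**What to change.** In 4.3 item 3, state that for Phase 2 the existing look-backs must also be met as of the Challenge Visit. In 8.3 item 3, require pre-challenge FEV1 of at least 80% predicted, taken from the spirometry already done, before the first spray. A child who fails FEV1 can be re-evaluated under 8.9, which allows this "if their condition improves within 2 months of the Screening Visit". Later failures, and failures of a look-back, go to rescreening under 8.2, which should name an asthma exacerbation as a reason. A challenge-day ACT is optional.

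The cost is protocol wording and one eCRF check. A child with an emergency visit or a steroid course is delayed by up to 3 months. Rescreening is open only while recruitment continues, so a late failure may be lost. A child who fails a 12-month or 2-year look-back is in practice excluded, because the planned study duration is 1 year. Participants discontinued before any dose may be replaced (6.4), so the target of 25 can still be reached.

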3.5. Symptom scoring

The systems for symptom scoring for use in tabulating clinical responses before or after allergen exposure are described in Table 3.5 and Figure 3.5.

[figure not shown]
[figure not shown]
[figure not shown]
[figure not shown]
[figure not shown]
[figure not shown]
Symptom scores will be assessed at the following time points or as described in the MOP for Protocol ICAC-27:

- Baseline – pre and post nasal rinse
- After each NAC dose administration

Table 3.5. Total Nasal Symptom Score (TNSS)

Category	Measurement	Points
Sneezing Sneeze Count = —	none	0
	1-2	1
	3-4	2
	5 or more	3
Runny nose	None - my nose feels fine and not runny at all	0
	Mild - my nose is a little runny; I might be able to blow a little snot or mucous out	1
	Moderate - my nose is very runny; I could definitely blow out some snot or mucous	2
	Severe - my nose is extremely runny; I could blow out a lot of snot or mucous	3
Stuffy nose	None - my nose feels fine; I am not at all stuffy or congested	0
	Mild - my nose feels a little stuffy	1
	Moderate - my nose feels very stuffy; it is hard to breathe through my nose	2
	Severe - my nose is completely stuffy; I cannot even breathe through my nose	3
Itchy Nose	None - my nose does not itch at all	0
	Mild - my nose feels a little itchy	1
	Moderate - my nose feels very itchy	2
	Severe - my nose is extremely itchy	3
TNSS		/12

Figure 3.5. Visual Analog Scale (VAS)

Nasal Symptoms:		
Sneezing		As Bad as I Can Imagine
No Symptoms		As Bad as I Can Imagine
Runny nose		As Bad as I Can Imagine
No Symptoms		As Bad as I Can Imagine
Stuffy nose		As Bad as I Can Imagine
No Symptoms		As Bad as I Can Imagine
Itchy nose		As Bad as I Can Imagine
No Symptoms		As Bad as I Can Imagine
Overall:		
No Symptoms		As Bad as I Can Imagine

Please mark with a single vertical (up and down) line for how you feel **RIGHT NOW for each symptom, as shown to you by the staff.**

4. Selection of Participants and Clinical Sites/Laboratories

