recruitment is ongoing, if their asthma can be brought under control, based on albuterol use, they are eligible for rescreening.

Participants may also qualify for rescreening if they are ineligible due to nasal symptoms or other reversible illness if their condition improves while recruitment is ongoing.

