8.3. Challenge Visit

Participants who are deemed eligible based on results from tests conducted at the Screening Visit will be invited to proceed to the Challenge Visit in Phase 1a and Phase 2.

The following procedures, assessments, and laboratory measures will be conducted:

1. Concomitant medications
2. Adverse events
3. Assessment of nasal and pulmonary symptoms (including spirometry)
4. Brief Physical Exam - includes Vital signs, height, weight and nasal and lung exam (or as specified in the MOP for Protocol ICAC-27)
5. Urine pregnancy test (female participants; if more than 28 days after the screening visit)
6. Initial nasal rinses – approximately 200mcl of isotonic saline solution (2 sprays) will be sprayed into each nostril and the participant will be asked to blow their nose; this process will be repeated 3 times (as specified in the MOP for Protocol ICAC-27). The fluids from the 2nd and 3rd rinses will be collected and processed for analysis as specified in the MOP for Protocol ICAC-27 – the outcomes from these fluids will be considered baseline for the ensuing nasal challenge procedure. A nasal rinse will be repeated 10 minutes after the diluent control is administered and after each dose of allergen during the NAC, as specified in the MOP for Protocol ICAC-27.
7. Nasal symptoms – TNSS and VAS and will be assessed pre and post the initial nasal rinses, and then 10 -20 minutes after each NAC dose administration and before the nasal rinse. (as specified in the MOP for Protocol ICAC-27) If the participant does not qualify for the Challenge because of the TNSS score, they may be rescheduled as per the MOP for Protocol ICAC-27.
8. Peak nasal inspiratory flow (PNIF) - assessed pre and post the initial nasal rinses, and then 10-20 minutes after each NAC dose administration (as specified in the MOP for Protocol ICAC-27)

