- Have past or current medical problems or findings from physical examination or laboratory testing that are not listed above, which, in the opinion of the investigator, may pose additional risks from participation in the study, may interfere with the participant's ability to comply with study requirements or that may impact the quality or interpretation of the data obtained from the study.
- Meet any of the Participant Stopping Rules and Withdrawal Criteria during Phase 1a
 - The participant elected to withdraw consent from all future study activities, including follow-up.
 - The participant died.
 - The Investigator no longer believes participation is in the best interest of the participant.
 - SAE related to investigational product
 - Anaphylactic reaction grade 2 or 3 (see Table 12.3.1c)
 - Inability to tolerate the NAC prior to reaching a TNSS ≥ 8 or sneezing score of 3 due to excessive discomfort or symptoms
 - Epistaxis occurring during the Challenge Visit

- The need to start immunotherapy or any chronic immunosuppressive medications in the period between Phase 1a and Phase 1b
- Require a dose of greater than 500 mcg of fluticasone per day or the equivalent of another inhaled corticosteroid to maintain asthma control in the period between Phase 1a and Phase 1b
- Inability to restrict use of antihistamines, nasal steroids, nasal decongestants, nasal anticholinergics or cromolyn prior to the NAC according to the period specified in the ICAC medication washout guidelines described in the MOP for Protocol ICAC-27
- Development of any serious medical illness whose natural history, sequela, or treatment would be worsened or impaired by continuation in the protocol
- Participant is “lost to follow-up,” as defined in the MOP for Protocol ICAC-27.
- The participant’s initial TNSS at the Repeat Challenge Visit must be within 1 point of the initial TNSS at the Challenge Visit in Phase 1a. If the participant’s initial TNSS is outside the 1 point range, then the participant may be reevaluated for the Repeat Challenge Visit up to 3 additional times.
- The Repeat Challenge Visit will proceed as described in Section 8.3, except that there will be an additional blood draw for mechanistic studies that will occur approximately 6 hours after the initiation of the challenge (or as specified in the MOP for Protocol ICAC-27). Nasal samples will be collected and processed for analysis as specified in the MOP for Protocol ICAC-27.

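### Exclusion criterion 5, as written, excludes only the baseline profile 1+1+1+1 and nobody with TNSS 5 to 12 or any symptom scored 2 or 3

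*Protocol*

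**What the plan says.** Item 5 belongs to a list in which meeting any one entry makes a person ineligible for Phase 1a and Phase 2. It reads: "Have active rhinitis symptoms prior to the nasal allergen challenge, defined as a Baseline TNSS >3 , with no individual symptom score >1". The Protocol synopsis and the SAP synopsis use the same wording, so this is not an extraction fault in one place.

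Protocol Table 3.5 builds the TNSS from four symptoms (sneezing, runny, stuffy and itchy nose), each scored 0 to 3, for a maximum of 12. Baseline is scored twice, "pre and post nasal rinse".

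Other sections assume that nasal symptoms or the TNSS can disqualify a candidate, but none gives a number:

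- Protocol 8.2: "Participants may also qualify for rescreening if they are ineligible due to nasal symptoms or other reversible illness".
- Protocol 8.3, item 7: "If the participant does not qualify for the Challenge because of the TNSS score, they may be rescheduled", with the details left to the Manual of Procedures.
- Protocol 8.4: "The Repeat Challenge Visit will proceed as described in Section 8.3, except that there will be an additional blood draw".
- Protocol 8.9: "Participants may be reevaluated up to a maximum of 2 times for the Phase 1a and Phase 2 Challenge Visits" and "Participants may be reevaluated up to a maximum of 3 times for the Phase 1b Repeat Challenge Visit", in both cases where nasal symptoms or another reversible illness caused the ineligibility.

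Two further items bear on baseline symptoms. Phase 1b exclusion 9 limits the repeat-visit starting score only relative to the Phase 1a score (within 1 point). Exclusion 11 is investigator judgement.

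**The concern.** The item opens by naming active rhinitis but defines it so that only one mild profile qualifies. It also runs backwards: raise any one symptom of 1+1+1+1 from 1 to 2 and the person is no longer excluded. It is the only absolute numeric baseline limit in the two documents, so nothing else shown does its work.

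The primary outcome depends on that limit. Under SAP 7.1.4 a positive response is an absolute score after a dose: TNSS of at least 8 in adults, at least 6 in children, or a sneezing score of 3. It is not a change from baseline. Protocol 13.4.2 and SAP 7.1.4 then count a responder as positive at every later dose.

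A participant who starts with a raised score can therefore cross the threshold with little allergen effect. One who is already at threshold, and whose symptoms persist, would stop at the diluent and count as positive at all nine doses.

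In Phase 2, a crossing at challenge dose 2 in one of the first five children would also keep that dose in the series (Protocol 3.1). That consequence is small, because later children would simply receive the full series already planned.

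**Working it through.** **Inputs.** Four symptoms, each an integer from 0 to 3 (Protocol Table 3.5). Item 5: total >3 and every score ≤1 (Protocol 4.3). Positive response: total ≥8 (adult) or ≥6 (child), or sneezing 3 (SAP 7.1.4). Planned cohorts: 10 adults and 25 children.

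**Check against the plan's own figure.** Maximum total = 4 × 3 = 12, which agrees with Table 3.5. Number of ordered profiles = 4⁴ = 256.

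**What item 5 catches.** If every score is ≤1, the total is at most 4 × 1 = 4. A total above 3 must then equal 4, which forces 1+1+1+1. Enumerating all profiles confirms this:

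| Set of profiles | Number | Excluded by item 5 |
|---|---|---|
| Total >3 | 221 | 1 |
| Total 5 to 12 | 190 | 0 |
| Any symptom scored 2 or 3 | 256 − 2⁴ = 240 | 0 |
| Every symptom ≥1 and at least one >1 | 3⁴ − 1 = 80 | 0 |

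Ignoring order, it excludes 1 of the 28 profiles with a total above 3. These counts show the logic of the rule. They are not shares of participants.

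**What it lets through.** Of the 221 − 1 = 220 profiles with a total above 3 that stay eligible on this item:

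- Child rule: 159 are already positive at baseline. The other 61 are 27 at TNSS 4 and 34 at TNSS 5.
- Adult rule: 97 are already positive. The other 123 are 27, 34, 34 and 28 at TNSS 4, 5, 6 and 7.

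**Smallest TNSS rise that makes a not-yet-positive participant positive.**

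| Reading of item 5 | Profiles left eligible | Child | Adult |
|---|---|---|---|
| As written | 255 | 6 − 5 = 1 | 8 − 7 = 1 |
| Exclude if total >3 and at least one score >1 | 256 − 220 = 36 | 6 − 4 = 2 | 8 − 4 = 4 |
| Exclude if total >3 | 35 | 6 − 3 = 3 | 8 − 3 = 5 |
| Exclude if total >3 or any score >1 | 15 | 6 − 3 = 3 | 8 − 3 = 5 |

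The last three rows are assumed readings, shown for scale. They differ in more than the smallest rise. For example, excluding on total >3 alone still admits sneezing 3 with all else 0, which already meets the positive-response definition. The last reading admits no profile that is already positive.

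**Effect on the primary proportion.** One participant counted this way adds 1/25 = 4 percentage points in children or 1/10 = 10 in adults. The addition applies at the dose of crossing and at each later dose, until the allergen alone would have produced a response.

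**The case against.** The strongest reply is that no site would apply the literal rule. The item's opening words, and Protocol 8.2, 8.3 and 8.9, all point to turning symptomatic people away. The final clause looks like an eligibility condition carried into an exclusion list, the Manual of Procedures may state a proper limit, and exclusion 11 gives the investigator a further stop. The documents do not show that anyone with a raised baseline was admitted. In Phase 1a no adult reacted at challenge dose 2, so there is no sign of early crossing there.

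The consequences are also bounded. The primary analysis is estimation without a hypothesis test, and a diluent step comes before any allergen. The per-subject listings, graphs and change-from-baseline displays in SAP 7.1.5 and 7.2.3 would show a crossing such as 5 to 6.

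Much of this stands, and it limits how serious the point is. It does not rescue the wording. The displays reveal a case but leave the primary proportion unchanged. Knowing that some limit was intended does not tell five sites which one, because the plausible repairs admit different people. If the Manual differs from the Protocol, sites hold two conflicting rules, while Protocol 15.1 permits no deviation from the Protocol.

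**Conclusion.** The concern holds. Item 5 is wrong as written: it excludes one mild profile and leaves eligible, on this item, every profile with TNSS 5 to 12 or any symptom scored 2 or 3. That contradicts its own opening words and the sections that treat nasal symptoms as disqualifying. It is best seen as a drafting error that weakens protection of the primary outcome, and it should be fixed; it does not invalidate the trial.

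The finding on the wording is arithmetic and rests only on Table 3.5 and the text of item 5. The size of any bias rests on two things the documents do not give: how often candidates arrive with raised scores, and what limit sites actually apply. The comparison with a corrected rule also depends on which reading the sponsor intended.

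The deciding score is a second gap. SAP 7.2.3 fixes the post-rinse value as baseline for the change scores only, so eligibility could be judged on either of two scores.

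**What to change.** Reword item 5 in the Protocol synopsis, Protocol 4.3 and the SAP synopsis so that it excludes what its opening words describe. At the same time:

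- Reconcile it with whatever limit the Manual of Procedures applies under Protocol 8.3.
- State whether the pre-rinse or the post-rinse TNSS decides eligibility.
- State whether the same limit applies at the Phase 1b repeat visit. Protocol 8.4 carries over the 8.3 procedures, but item 5 is listed only for Phase 1a and Phase 2.
- Record which limit sites used in Phase 1a, so that readers can see whether adults and children entered under the same baseline rule.

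The sponsor should settle the replacement rule after that reconciliation. One reading that keeps both existing cut-offs, for the sponsor to confirm or reject, excludes on a total above 3 or any single score above 1.

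**Cost.** The two Protocol copies need an amendment by the route in Protocol 16.2 (IND sponsor and IRB approval, and FDA submission). That section does not mention the SAP, whose copy needs its own revision. Phase 1a is complete, so the change can affect only Phase 2 and any remaining Phase 1b visits. If sites have been admitting symptomatic candidates, some would be rescheduled or lost. Protocol 8.9 allows at most 2 re-evaluations, within 2 months of screening, for Phase 1a and Phase 2, although 8.2 also allows rescreening while recruitment is open. If Phase 1a used a different limit, the cohorts would be slightly less comparable.
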